2.2. Scientific Rationale

Study Proposal: This is an uncontrolled two-arm open-label single-center interventional clinical trial that will be used to prepare for a full-scale randomized, placebo-controlled trial by investigating the feasibility of the study and proposed measures collection. It will explore changes in SzNET, RSNs, and EEG data, before, and after combination drug therapy with levetiracetam and phenobarbital (or a combination of two other ASM drugs (see section 4.1) and psychometric measures at 3 months after hospital discharge based on a sample of 54 patients with MSABI and DoC. Our long-term goal for this research line is to determine if SzNET are linked to epileptogenic activity in SABI to improve the endotype characterization of its DoC and better guide targeted treatments.

Rational for specific aims and outcome measures: The purpose of this study is to determine the occurrence of a specific biomarker called SzNET in patients with MSABI and investigate the effects of ASM on SzNET. The study also aims to find any correlation between EEG and SzNET in patients who experience seizures on EEG.

The study outcome measures will focus on quantifiable changes in SzNET and RSNs with therapy. It is difficult to isolate the effects of early therapy on outcomes due to the high rate of withdrawal of life sustaining therapy in the early weeks of MSABI and the potential secondary injuries. Therefore, this study will take a conservative approach and focus on quantifiable changes in SzNET and RSNs with therapy. If there are no significant changes in the networks after therapy, it may not be necessary to further investigate the relationship between SzNET and outcomes. The feasibility of collecting outcomes and trends in relation to SzNET will be tested as part of this pilot study through ICU exams and follow-up clinics, including side effects of medication, morbidity, and mortality, to identify any positive trends.

Rational for study inclusion/exclusion criteria: This study focuses on patients with brain damage severe enough to impair consciousness but with the potential to recover in the absence of epileptogenic activity. The inclusion criteria have been chosen to identify patients with this level of brain damage.

To be eligible for the study, patients must have a suppression of consciousness related to a neurological injury with Glasgow Coma Scale of less than 13 and be hospitalized at the ICU. This brain injury severity score indicates that the patient has a moderate to severe consciousness compromise, which is the intended target population. Patients who have recovered their baseline mental status or the ability to follow commands prior to therapy are excluded from the study or withdrawn if they were already consented into the study. This exclusion ensures that eligible participants still has a disorder of consciousness severe enough to warrant the risk of the study therapy. Patients who are brain dead are also excluded from the study because their lesions are so severe that recovery is not possible, regardless of the treatment.

Rational for study intervention:

The relationship between SzNET, EEG, and epileptogenic activity in patients with MSABI is not yet fully understood. To validate SzNET, it is necessary to explore its meaning in patients who are EEG-negative, as they are the population that could potentially benefit from it the most, given the possibility of epileptogenic activity overlooked by EEG. Validating seizure-biomarkers in surface EEG-negative patients is challenging, as the alternative gold standard validation methods should be the intracranial EEG which would propose higher risk in the target population for increased bleeding and infection risks. By administering an ASM and observing the induced changes in SzNET and RSN we may document a response like the observed in the patients referenced in table 2. If we can gather

preliminary information consistent with our pilot findings, that may justify conducting a larger randomized controlled trial (RCT).

Rational for two ASMS and dosage:

When the EEG is positive, we can track a patient's response to medication, but we won't have a similar bedside measure of immediate improvement in patients who are EEG-negative but have positive SzNET. If SzNET is contributing to a patient's depressed mental status as occurs during non convulsive status epilepticus, Its severity could be similar.

Since we cannot measure improvement by EEG, and because more than one medication is often required in status epilepticus, we need a strategy with a high likelihood of controlling epileptogenic activity. Dual loading doses of ASM have been shown to provide a more definitive response in known cases of status epilepticus than using only one medication^{23,24}. The selection of phenobarbital is due to its relatively high efficacy in status epilepticus^{25,26}. The primary concerning side effect of phenobarbital is ventilatory depression. However, this effect is less relevant in this population as many of these patients already have a secure airway due to the ongoing depression in mental status and required mechanical ventilation. Therefore, this is not a significant concern for patients who are already under mechanical ventilation due to their low neurological response.

3. Specific Aims

3.1. Aim 1

Obtain a preliminary estimate of the seizure networks (SzNET) changes in moderate to severe acute brain injury (MSABI) patients after the research intervention with antiseizure medication (ASM) to support a future larger placebo controlled resting state-fMRI (rs-fMRI) clinical trial for prediction models of epileptogenicity in early SABI. The preliminary data of primary interest is the magnitude of the functional imaging SzNET response to high-efficacy pharmacological treatments in this clinical setting.

Aim 1a

Measure the improvement of the SzNET spatial total volume ([TV](#)) in MSABI patients after the intervention. The estimand of interest is the SzNET spatial TV median before and after the intervention in the target population. The intrasubject TV change ratio will be expressed as total volume reduction ([TVR](#)).

Aim 1b

Measure the improvement of the SzNET temporal power spectrum ([PS](#)) in MSABI patients after the intervention. The estimand of interest is the SzNET temporal PS median before and after the intervention in the target population. The intrasubject PS change ratio will be expressed as power spectrum improvement ([PSI](#))

3.2. Aim 2

Estimate the frequency of EEG- and EEG+ patients presenting with SzNET on their initial rs-fMRI prior to the study intervention. The estimands of interest are the proportions and differences of proportions of patients with SzNET among EEG- and EEG+ patients in this clinical setting.

3.3. Aim 3

Investigate association between post-intervention EEG improvement and SzNET response. The estimand of interest is the relative risk of EEG improvement in patients with more than 50% improvement of their SzNET by TVR and PSI.

3.4. Aim 4

Investigate the association between the post-intervention typical resting state networks (RSN) connectivity improvement and the SzNET response. The estimand of interest is the relative risk of improvement of the RSNs in the patients with more than 50% of improvement of their SzNET by TVR and PSI.

3.5. Aim 5

Describe psychosocial functional measure outcomes and ambulatory ASM toxicity at 3 months from hospital discharge. The estimates of interest will be the PROMIS Emotional Distress—Anxiety— Short Form, the Neurological Disorders Depression Inventory for Epilepsy (NNDI-E), the QOLIE-10-P, the Telephonic Montreal Cognitive Assessment, and the Liverpool adverse event profile test. All will be assessed at the 3 month follow up visit by one of the NSICU Post-Discharge clinics. This aim only applies to the patients that are discharged alive from the hospital and will include results from visits until 14 months after the enrollment start.

3.6. Aim 6

Assess the trial's design feasibility success in enrollment and retention for our actual institutional context by evaluating the enrollment rate and dropout rate among participants at the end of the trial. It will be composed by two sub aims.

Aim 6a

Measure the participants enrollment rate during the hole study enrolling months. The estimand of interest will be the rate of enrolled patients per month.

Aim 6b

Measure the participants dropout rate among participants. The estimand of interest will be the dropout rate from the total enrolled participants at the end of the study.

4. Study Design

This is a prospective interventional, uncontrolled, open-label, single center pilot study in moderate to severe acute brain injury (MSABI) patients with suppression of consciousness. The study main outcomes require pre and post-intervention rs-fMRI data collection to characterize the evolution of SzNET, a physiological measure of brain function. Clinical implementation of rs-fMRI is still novel, not frequently performed at early stages of MSABI, and has few medical indications as a follow-up test. As this data is infrequently generated during the standard of care (SOC), a prospective interventional study with an ASM intervention and a research funded rs-fMRIs is needed.

The target population is in the UNC intensive care unit, and to prioritize the human subjects' wellbeing, the patients will receive their standard clinical monitoring and therapy per the local care team, including EEG, antiseizure therapy, and head imaging as clinically indicated. Once stable for MRI, subjects will receive the study-related rs-fMRI #1. If SzNET are detected (SzNET+), the subject will start the study treatment protocol, followed by post-treatment repeat rs-fMRI (rs-fMRI#2) and EEG. Those patients negative for SzNET in the rs-fMRI#1 (SzNET-) will not

have intervention or research follow up EEG and rs-fMRI, but if they are followed by one of the NSICU Post-Discharge clinics, the information obtained from their assessments will be collected as part of this study.

Rationale for intervention with ASM

The purpose of this study is to test the correlation of SzNET in MSABI with epileptogenic activity. To benchmark this correlation, we will compare the response of SzNET to ASM with well-known effect in the epileptogenic activity. Previous data in epilepsy shows that SzNET improvement is related to clinical improvement¹³, and those clinical effect sizes of seizure improvement have been measured for multiple pharmacological treatments including the ones listed for this protocol intervention^{26,27}. We hypothesize that SzNET improvement will be similar to the effect size expected for the selected ASM. If we are correct, SzNET could help predict clinical outcomes related to epileptogenic activity. To achieve this, we need treatment protocols with proven consistent clinical response and a large effect size. The recommended protocol for a effective response is a combination of intravenous phenobarbital and levetiracetam at loading doses²⁶. However, since the main outcome measures are quantitative and smaller effect size responses could still be detected, for this pilot trial we allow a list of alternative ASM protocols with anticipated similar efficacy. The purpose of this alternative options is that the care team can use a different protocol if it is more appropriate given the patient's particular characteristics.

Rationale for stratification by EEG

Restated: Seizure network activity could be the cause of suppressed conscious in acute brain injury. The EEG, which is the best current test for detection of seizure, may not detect this activity, if it is occurring in deep brain locations. SzNET by rs-fMRI may be a biomarker of abnormal activity in acute brain injury that could be responsive to ASM. In ICU patients with suppression of consciousness, we will use the EEG to stratify patients into two groups, EEG+ and EEG-. EEG+ will be defined by either electrographic seizure, electroclinical seizure or ictal-interictal continuum as defined by the American clinical Neurophysiology Society's Standardized Critical Care EEG Terminology²⁸, whereas EEG- will be lacking these features. Further, we will observe the rate of SzNET by rs-fMRI in both groups, and response of the SzNET and EEG to study intervention.

To ensure rapid recruitment, the study will use a quota sampling strategy. Specifically, eleven SzNET+ patients will be recruited consecutively for each EEG+ and EEG- strata to ensure the necessary number of patients for the interventional phase of the study.

Data collection

First, informed consent will be obtained from the subject's legally authorized representative (LAR). Then, baseline variables will be collected by interview and review of medical charts. After subjects are scanned, the rs-fMRI images are uploaded to the UNCH MRI PACS system by an MRI technician and accessed through the UNCH secure PACS portal by study personnel, through download onto the UNC SOM secure system. There, the rs-fMRI processing and analysis are accomplished, and information is deidentified for storage in the PI's UNC-OneDrive. Clinical and demographic data will be collected by the study research coordinator and stored in a REDCap file. Once the study data collection is completed, the deidentified REDCap database will be used for analysis and stored at the PI's UNC-OneDrive. A separately stored subject key code in a SOM-stored research excel file will link the research subject's codes and MRN until five years after study completion. Hospital discharged patients will be followed through one of the NSICU Post-Discharge clinics, and that data will be stored in the same study REDCap file.

End-of-study criteria and discontinuation criteria for the participant.

Patients that need to discontinue the study treatments during the intervention phase because of medical reasons will be withdrawn from the study, unless they can be assigned to one of the alternative combination-drug protocols and continue to meet eligibility criteria.

[figure not shown]
End-of-study criteria or stopping-rules for the entire study.

If a severe adverse event related to study participation occurs (e.g., transportation to the MRI scan, side-effect of the ASM intervention), the study will be suspended pending review by the IRB and implementation of an approved Corrective and Preventative Action Plan.

Based on pilot data, SzNET is common in patients who are EEG+, but only present in about 30% of patients who are EEG-. After enrolling 40 patients, we will review the results of rs-fMRI #1, and the study will stop because of futility if we observe one of the following criteria:

- SzNET are detected in less than 70% of the patients classified as EEG+ or less than 10% of the patients in the EEG- group.
- More than 50% of the subjects from the intervention group do not show a change in SzNET after the study treatment.

Figure 2. Study Flow Diagram.

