5.1. Numbers of Participants

5.1.1. Number to be screened: N=68

5.1.2. Number to be enrolled: N = 54

Rationale of Number Expected to be Screened:

The Study will employ a quota sampling method to enroll four groups of patients, designated as: SzNET+/EEG+, SzNET+/EEG-, SzNET-/EEG+, and SzNET-/EEG-. Importantly, only the two SzNET+ groups have a minimum enrollment goal. Thus, enrollment will stop once each of the two SzNET+ groups enroll ten patients. The logic behind the patient screening and enrollments is as below.

1. SzNET+/EEG- Strata: To successfully complete the study treatment in 10 EEG- subjects, who would eventually be found to be SzNET+, we need to enroll 11 subjects, as we anticipate a 1 in 10 subject attrition. In our preliminary SABI data (Fig 2), of those who would meet inclusion/exclusion criteria, 30% with EEG- were SzNET+. Thus, we expect to need to enroll approximately 37 EEG- patients with completed good quality studies. Lastly, due to the ICU environment and the Barthel score required, we expect 80% of the subjects eligible for enrollment, thus 46 EEG- patients will be screened to fulfill this group's recruitment goal.

2. SzNET+/EEG+ Strata: To successfully complete treatment in 10 EEG+ subjects, who would eventually be found to be SzNET+, we need to enroll 11 patients, as we anticipate a 1 in 10 subject attrition. In our preliminary SABI data (Fig 2), of those who would meet inclusion/exclusion criteria, 67% of the EEG+ were SzNET+. Thus, we expect to need to enroll approximately 17 EEG+ patients with completed good studies. Lastly, due to the ICU environment and the Barthel score required, we expect 80% of the subjects eligible for enrollment. Thus, 22 EEG+ patients will be screened to fulfill this group's recruitment goal.

Participants who drop out, are withdrawn, or have missing data will not be replaced until second aim's data is complete, afterwards we will continue recruitment until we meet the two strata proposed enrollment. The subjects analyzed for the second aim will only include those scanned until the time when the first group of SzNET+/EEG+ or SzNET+/EEG- recruitment will be completed. By this strategy, the initial estimate of the proportion of SzNET+ subjects by EEG subgroup could be less biased, and we will guarantee the required number of subjects to start the interventional phase of the study while optimizing the total amount of initial rs-fMRI needed.

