5.2.1. Inclusion Criteria

[figure not shown]

Fig. 1. Adult and Peds SABI EEG and Seizure Network (SN) prevalence (N=63). EEG-SN+ comprise 30% of the SABI population.

In order to be eligible to participate in this study, an individual must meet all of the following criteria:

- Age from 18 months to 70 years at ICU admission by medical chart review.
- Suppression of consciousness related to a neurological injury by medical chart review.
- GCS less than 13 at enrollment.
- Diagnosis of Acute brain injury by TBI, hypoxic-ischemic insult, cardiac arrest or stroke by medical chart review.
- 2 to 90 days from acute brain injury to enrollment time by medical chart review.
- Have a routine clinical surface EEG performed after the admission to PICU, NSICU, SICU, CTICU, CICU or MICU.
- Clinically stable to undergo MRI scan, This stability is defined by care team concept, which should be stated in the medical records.
- Hospitalized in NSICU, PICU, SICU, CTICU, CICU or MICU

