8.4. Planned Interim Analyses

No interim analyses will be performed.

9. Sample Size Rationale

There is no preliminary data for effect size estimation using the paradigm and patient population suggested in this study. In Aim 1, a paired t-test is used to test measurement differences before and after ASM. A effect size 0.806 can be detected for a 1-sided test at a power of 80% and a Type I error at 0.05 with the total of 11 subjects before and after ASM. In Aim 4, a transformed Z-test is used to test correlation between two variables. A correlation size 0.506 can be detected for a 1-sided test at a power of 80% and a Type I error at 0.05 with the total of 22 subjects.

10. Data Capture and Database Management

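### The 70% futility boundary for EEG+ patients lies above the plan's own 67% planning rate, so the 40-patient rule triggers in about half of trials when the assumptions are right, and Section 8.4 denies any interim analysis

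*Combined protocol and SAP*

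**What the plan says.** - **Section 4, stopping rules for the entire study.** "After enrolling 40 patients, we will review the results of rs-fMRI #1, and the study will stop because of futility" if any listed criterion is met. The first criterion is that "SzNET are detected in less than 70% of the patients classified as EEG" positive, or in under 10% of EEG- patients. The second is that over half of the treated patients show no SzNET response. The rule is introduced with the remark that SzNET is common in EEG+ patients and present in about 30% of EEG- patients.
- **Section 5.1, sample size.** The EEG+ stratum rests on preliminary data in which "67% of the EEG+ were SzNET" positive. The EEG- stratum rests on 30%.
- **Quotas.** Section 4 says that "eleven SzNET+ patients will be recruited consecutively for each EEG+ and EEG- strata". Section 5.1 says that "enrollment will stop once each of the two SzNET+ groups enroll ten patients".
- **Section 8.4.** "No interim analyses will be performed".

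Nowhere does the protocol explain why the boundary is 70% when the planning rate is 67%, call 70% a deliberate minimum, or give the probability that the rule triggers.

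**The concern.** A futility boundary should rarely be crossed when the design assumptions hold. Here the EEG+ boundary is three percentage points above the assumed rate, so an observed proportion equal to the assumption already counts as futile. The EEG- boundary is set the other way, 20 points below its planning rate, which suggests that 70% was not chosen with the 67% in view.

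At stake is a pilot meant to inform a larger trial. It could be labelled futile although its prevalence assumption was correct, and lose part of the SzNET+ group on which Aims 1, 3 and 4 depend.

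Section 8.4 adds a second problem. The review looks at SzNET presence (the Aim 2 outcome) and at post-treatment SzNET change (the subject of Aim 1), and it can end the study, yet the analysis plan says no such look exists.

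**Working it through.** **1. Are 67% and 30% the rates the plan is built on?** Divide the quota of 11 by each rate (Section 5.1): 11/0.67 = 16.4, rounded up to 17 EEG+; 11/0.30 = 36.7, rounded up to 37 EEG-. The total is 54, the stated target. For screening, 17/0.80 = 21.25 (stated 22) and 37/0.80 = 46.25 (stated 46), which gives 68. The plan's figures reproduce.

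**2. Exact probability for the EEG+ limb.** With n EEG+ patients at the review, the limb triggers when X < 0.70n, X ~ Binomial(n, 0.67). The protocol does not give n. The planned mix implies 40 × 17/54 = 12.6.

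| EEG+ patients at review | SzNET+ needed to continue | P(trigger), true rate 67% |
|---|---|---|
| 10 | 7 | 0.43 |
| 12 | 9 | 0.60 |
| 13 | 10 | 0.67 |
| 17 | 12 | 0.51 |

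Over n = 8 to 24 the range is 0.43 to 0.68.

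**3. Sequential enrolment with quotas.** Simulation rules: enrol one patient at a time; when one SzNET+ quota fills, enrol only the other EEG stratum; end when both fill; apply the rule at patient 40. True rates are 67% (EEG+) and 30% (EEG-). The EEG+ share is an assumption, varied from 19% to 50%.

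| Quota per stratum | Trials reaching 40 | Trigger, of trials reaching 40 | Trigger, of all trials |
|---|---|---|---|
| 11 | 94% | 0.56-0.61 | 0.52-0.57 |
| 10 | 83% | 0.56-0.59 | 0.47-0.49 |

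The EEG- limb adds only 0.2-0.3 percentage points, so the EEG+ boundary drives the result. The post-treatment criterion is left out because no response rate is given; it could only raise these figures.

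**4. A different reading of the pilot data.** The Fig. 1 caption says that "EEG-SN+ comprise 30% of the SABI population", a share of all patients and not of EEG- patients. On that reading, with 27 of 63 patients SzNET+ (Section 2.1):

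- 0.30 × 63 ≈ 19 are EEG-/SzNET+, and 27 − 19 = 8 are EEG+/SzNET+.
- 8/0.67 ≈ 12 are EEG+, a share of 12/63 = 19%.
- The EEG- rate is 19/51 = 37%.

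At a 37% EEG- rate and a 19% share, the rule triggers in 0.61 (quota 11) or 0.65 (quota 10) of trials that reach 40, and in 0.49 or 0.39 of all trials.

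**5. How high must the true EEG+ rate be?** Among trials that reach 40, with the EEG- rate at 30%:

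| True EEG+ rate | Trigger probability |
|---|---|
| 75% | 0.30-0.37 |
| 80% | 0.16-0.24 |
| 85% | 0.06-0.13 |
| 90% | 0.02-0.06 |

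**6. What a stop leaves.** With the EEG- rate at 30%, the mean number of SzNET+ patients accrued at a trigger is 14.1-17.0 (5th to 95th percentile 9-21), against 22 planned. The detectable Aim 1 effect (one-sided paired t-test, alpha 0.05, power 80%, before attrition) is 0.806 for n = 11, which reproduces Section 9. It is 0.702 for n = 14, 0.630 for n = 17 and 0.548 for n = 22.

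**The case against.** - **70% may be intended.** If SzNET is not frequent where seizures are visible on EEG, its value as a seizure marker is in doubt, so a minimum yield is a legitimate go/no-go standard. The 67% is a recruitment input, not a target. This stands as a possible rationale, but the protocol does not state it or the resulting stop probability.
- **The rule may be discretionary.** Section 13.2 uses permissive wording about stopping rules and allows the study to resume. Section 12.5 does not list the 40-patient rule. Section 4 nevertheless reads as mandatory. The figures are trigger probabilities; they are stop probabilities only if the rule is binding.
- **The harm is moderate.** True. Even after a stop, the detectable effect of 0.63-0.70 is better than the 0.806 in Section 9.
- **The inputs are uncertain.** The EEG+ share at the review is not documented, and some of the 40 may lack a usable first scan. This moves the figure but not the conclusion: the exact range is 0.43-0.68 for n = 8 to 24.
- **Section 8.4 is only a wording conflict.** The review involves no hypothesis test and one cross-reference would settle it. That is fair, and it adds little to the severity.

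**Conclusion.** The concern holds and should be fixed. The EEG+ boundary exceeds the rate used to size that stratum. With the planning rates exactly right, the rule triggers in roughly half of trials: 47-57% of all trials at 67% and 30%, and 39% in the lowest sensitivity case. The result rests on an assumed EEG+ share of 19-50%, on all 40 patients having a usable first scan, and on the rule being applied as written. Section 8.4 contradicts the review that Section 4 schedules. The consequence is a truncated pilot with a misleading futility label, not the loss of its aims.

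**What to change.** 1. In Section 4, do one of the following: justify 70% as a deliberate minimum and state that it triggers about half the time at a true 67%; set the EEG+ boundary clearly below 67%; or delete that limb. For any boundary kept, give its trigger probability at 67% and at a rate the sponsor would call futile.
2. Say whether the rule is binding, and align Section 13.2 with it.
3. Replace the statement in Section 8.4 with text such as: *One futility review is planned after 40 enrolments (Section 4). It uses SzNET presence on rs-fMRI #1 by EEG stratum and post-treatment SzNET change, without a hypothesis test.*

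The boundary is the sponsor's choice. For illustration, among trials that reach 40:

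| True EEG+ rate | <70% (current) | <50% | <40% |
|---|---|---|---|
| 67% | 0.56-0.61 | 0.06-0.13 | 0.02-0.06 |
| 50% | 0.87-0.95 | 0.44-0.47 | 0.19-0.27 |
| 30% | close to 1 | 0.86-0.96 | 0.72-0.83 |

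**Cost.** Text edits only, but a lower boundary gives fewer stops at intermediate true rates, as the 50% row shows. At a true 60% with 12-13 EEG+ patients, triggering falls from 78-83% to 16-23% (<50%) or 6-10% (<40%).

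Enrolment is random under quota sampling. With quota 11 at the planning rates, the mean needed to fill both quotas is 53.1. In the trials that a lower boundary would let continue, the mean is about 55, and 47-50% need more than 54. That overshoot comes from the existing quota design, but the sponsor should say whether 54 is a cap. At a true 50%, filling the EEG+ quota takes about 11/0.50 = 22 EEG+ patients instead of 17.
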